1 PROTOCOL SUMMARY

1.1 Synopsis

Title of Study:

A Phase 1 Randomized, Placebo-controlled Study to Assess the Safety, Tolerability and Pharmacokinetics of Multiple Doses of ASP8062 with a Single Dose of Morphine in Recreational Opioid Using Participants

Planned Study Period/Duration:

2Q2020 to 4Q2020

Planned Total Number of Study Sites and Location(s):

One study site in the US

Study Objectives, Endpoints and Estimands:**Objectives and Endpoints**

[figure not shown]
Objectives	Endpoints
Primary	
• Nature, frequency and severity of AEs• Clinical laboratory tests (hematology, biochemistry and urinalysis)• Vital signs (blood pressure, pulse and respiratory rate)• 12-lead ECG• C-SSRS• SpO₂• End tidal CO₂
Secondary	
• Plasma ASP8062: AUC₂₄ and C_{max}• Plasma morphine and its metabolites (M3G and M6G): AUC_{inf}, AUC_{last} and C_{max}
Exploratory	
• Oral temperature• ARCI-49• Plasma ASP8062: CL/F, t_{1/2}, t_{max}, t_{lag}, V_z/F, C_{trough} and PTR• Plasma ASP8062 metabolites (AS3486189, AS3486191 and AS3486192): C_{max}, AUC₂₄, t_{1/2}, t_{max}, t_{lag}, V_z/F, C_{trough} and PTR• Plasma morphine and its metabolites (M3G and M6G): AUC_{inf}(%extrap), CL/F (morphine), t_{1/2}, t_{max}, t_{lag} and V_z/F• Plasma ASP8062 metabolites (AS3486189, AS3486191 and AS3486192): AUC₂₄ and C_{max}

AE: adverse event; ARCI-49: 49-item short form of Addiction Research Center Inventory scale; CO₂: carbon dioxide; C-SSRS: Columbia-suicide severity rating scale; ECG: electrocardiogram; M3G: morphine-3β-D-glucuronide; M6G: morphine-6β-D-glucuronide; SpO₂: blood oxygen saturation

Estimands: Not applicable.																								
Study Population: This study will enroll male and female participants (18 to 60 years of age, inclusive) who have at least 10 lifetime uses of a recreational opioid drug with at least 1 opioid use in the last 90 days.																								
Number of Participants: Approximately 24 male and female participants to complete at least 18 participants. An attempt will be made to enroll 1 female participant for every 3 male participants.																								
Study Design Overview: This will be a randomized, participant- and investigator-blinded, placebo-controlled, single sequence study comprising of male and female recreational opioid-using participants. Participants will be screened for up to 28 days prior to first investigational product administration. Eligible participants will be admitted to the clinical unit on day -1 and will be residential for a single period of 17 days/16 nights. After randomization, participants will receive multiple oral doses of ASP8062 or placebo (2:1 ratio) on days 1 through 10. On day 10, all participants will also receive a single oral dose of morphine immediately after the ASP8062 or placebo dose followed by a 144-hour in-house blood sampling period. Scheduled safety and tolerability assessments will be conducted as indicated in the Schedule of Assessments Table 1 . Participants are to remain awake, seated or semirecumbent and avoid lying on either the left or right side for at least 4 hours postdose on days 9 and 10. Participants will be discharged from the clinical unit on day 16 on the condition that all required assessments have been performed and that there are no medical reasons for a longer stay in the clinical unit. The study will be completed with an end-of-study visit (ESV). The ESV will take place 5 to 9 days after the day 16 pharmacokinetic sample is collected or at early discontinuation/termination from the study.																								
Treatment Groups and Duration: 

Arm/IP Name	ASP8062	Placebo ASP8062	Morphine sulfate	

Use	Test product	Placebo for ASP8062	Test product	

Dose	25 mg (1 × 25 mg tablet)	NA (1 × tablet)	45 mg (3 × 15 mg immediate-release tablets)	

Frequency	Once daily	Once daily	Single dose	

Route	Oral	Oral	Oral	

Duration	10 days	10 days	1 day	

 IP: investigational product; NA: not applicable The anticipated duration of the study for each participant, including screening and follow-up, is approximately 53 days.	Arm/IP Name	ASP8062	Placebo ASP8062	Morphine sulfate	Use	Test product	Placebo for ASP8062	Test product	Dose	25 mg (1 × 25 mg tablet)	NA (1 × tablet)	45 mg (3 × 15 mg immediate-release tablets)	Frequency	Once daily	Once daily	Single dose	Route	Oral	Oral	Oral	Duration	10 days	10 days	1 day
Arm/IP Name	ASP8062	Placebo ASP8062	Morphine sulfate																					
Use	Test product	Placebo for ASP8062	Test product																					
Dose	25 mg (1 × 25 mg tablet)	NA (1 × tablet)	45 mg (3 × 15 mg immediate-release tablets)																					
Frequency	Once daily	Once daily	Single dose																					
Route	Oral	Oral	Oral																					
Duration	10 days	10 days	1 day																					

1.2 Study Schema

Figure 1 Study Schema

ESV: end-of-study visit

30 Jul 2020

Version 1.1 Incorporating Nonsubstantial Amendment 1

Astellas

Page 13 of 105

1.3 Schedule of Assessments

Table 1 Schedule of Assessments

Study Phase	Screening Period ¹		Investigational Period								Follow-up Period/ET
	Day(s)	-28 to -2	-1	1	2 to 8	9	10	11	12 to 15	16 ^{2,3}	
Residential Period		X		X	X	X	X	X	X	X	
Informed Consent		X									
Inclusion and Exclusion Criteria		X	X								
Randomization ⁵			X	(X)							
Demographics		X									
Medical History		X	X								
Drug Use History/TLFB ⁶		X	X								
Body Weight and Height ⁷		X	X							X	X
Clinical Laboratory Tests ⁸		X	X	X	X	X	X	X	X	X	X
Drugs of Abuse/Alcohol Tests		X	X								
Pregnancy Test (Female Participants Only) ⁹		X	X								X
FSH Test (Postmenopausal Female Participants Only)		X									
Vital Signs ¹⁰		X	X	X	X	X	X	X	X	X	X
Continuous Pulse Oximetry ¹¹						X	X				
12-lead ECG ¹²		X	X	X		X	X			X	X
Physical Examination ¹³		X	X			(X)				(X)	X
Spot SpO ₂ ¹⁴				X		X	X				
C-SSRS ¹⁵		X	X			X				X	X
ARCI-49				X		X	X	X			
Continuous and Spot End Tidal CO ₂ ¹⁶						X	X				

Table continued on next page

Study Phase	Screening Period ¹		Investigational Period							Follow-up Period/ET
	Day(s)	-28 to -2	-1	1	2 to 8	9	10	11	12 to 15	16 ^{2,3}
Blood sampling for Biomarker Analysis ¹⁷		X	(X)							
Blood Sampling for PGx Analysis ¹⁷		X	(X)							
Dosing ASP8062 or Placebo ¹⁸			X	X	X	X				
Dosing Morphine ¹⁹							X			
Blood Sampling for ASP8062 and its Metabolites (AS3486189, AS3486191 and AS3486192) Pharmacokinetics						X	X	X	X	X
Blood Sampling for Morphine and its Metabolites (M3G and M6G) Pharmacokinetics							X	X	X	
Adverse Event Assessment	X	X	X	X	X	X	X	X	X	X
Previous/Concomitant Medications	X	X	X	X	X	X	X	X	X	X

ARCI-49: 49-item short form of Addiction Research Center Inventory scale; CO₂: carbon dioxide; C-SSRS: Columbia-suicide severity rating scale; ECG: electrocardiogram; ESV: end-of-study visit; ET: early termination; FSH: follicle-stimulating hormone; M3G: morphine-3β-D-glucuronide; M6G: morphine-6β-D-glucuronide; PGx: pharmacogenomic; SpO₂: blood oxygen saturation; TLFB: timeline follow-back

1. Screening period is days -28 to -1. Eligibility will be confirmed at screening and on day -1. Participants who do not meet eligibility criteria on day -1 are considered screen failures.
2. Scheduled sampling up to day 16 (144 hours postdose of morphine).
3. Participants will be discharged from the clinical unit on day 16 on the condition that all required assessments have been performed and that there are no medical reasons for a longer stay in the clinical unit. If a participant discontinues early from the study, discharge/ESV procedures will be performed upon discontinuation.
4. The ESV will take place 5 to 9 days after the day 16 pharmacokinetic sample is collected or at early discontinuation/termination from the study.
5. Randomization can occur on day -1 or predose on day 1 provided that eligibility is confirmed prior to randomization.
6. TLFB will be collected for 2 weeks prior to screening or on day -1 (prior to any assessments).
7. Height to be collected at screening only.
8. Clinical laboratory tests include blood collection for serology (at screening only), hematology and biochemistry and urine collection for urinalysis.
9. Serum pregnancy test at screening and urine pregnancy test on day -1 and at the ESV.
10. Vital signs include measurements of blood pressure, pulse, respiratory rate and oral temperature. Measurements will be taken after the participant has been resting in the supine position for at least 5 minutes. Measurements will be taken in duplicate at screening and on day -1 and at all other time points as single measurements.

Footnotes continued on next page

11. Continuous pulse oximetry will begin predose on days 9 and 10 until at least 8 hours postdose..
12. 12-lead ECGs will be taken after the participant has been resting in the supine position for at least 5 minutes. 12-lead ECGs will be taken in triplicate.
13. Symptom-directed physical examinations may be performed on days 9 and 16. Full physical examinations will be performed at screening, day -1 and ESV.
14. Single SpO₂ measurements will be taken at designated time points.
15. The version of the C-SSRS to be performed at screening is the “Baseline/Screening” and the version of the C-SSRS to be performed on days -1, 9 and 16 and at the ESV is the “Since Last Visit”.
16. Continuous and spot end tidal CO₂ to be collected starting predose on days 9 and 10 until 8 hours postdose. Time points will be recorded predose and 1, 2, 4 and 8 hours postdose. The cannula may be removed while participants dose or eat.
17. The blood sample for biomarker and PGx analysis (biobanking) can be collected on day -1 or predose on day 1.
18. On days 1, 9 and 10, ASP8062 or placebo will be administered orally under fasting conditions (i.e., no food or beverage will be allowed from at least 10 hours predose through at least 4 hours postdose) with approximately 240 mL water. Water intake will be prohibited from at least 1 hour predose through at least 1 hour postdose, except for the approximately 240 mL water to swallow the investigational product. On all other dosing days, ASP8062 or placebo will be administered orally under standardized fed conditions (i.e., meals will be served up to 1 hour predose or at least 2 hours postdose) with approximately 240 mL water. Water intake will be allowed ad libitum.
19. On day 10, morphine will be administered as a single oral dose under existing fasting conditions with approximately 240 mL water, immediately after the ASP8062 or placebo dose. Water intake will be prohibited from at least 1 hour predose through at least 1 hour postdose, except for the approximately 240 mL water to swallow the investigational product.

Table 2 Sample Collection Schedule

Day	Time Point	Pharmacokinetics ASP8062/metabolites	Pharmacokinetics Morphine/metabolites	Vital Signs	Clinical Laboratory Tests	12-lead ECG	ARCI-49	Spot End Tidal CO ₂	Spot SpO ₂
Days -28 to -2	Screening			X	X	X			
-1				X	X	X			
1	Predose			X	X	X	X		X
	2 hours								
2	Predose								
	2 hours								
3	Predose			X	X				
	2 hours								
4	Predose								
	2 hours								
5	Predose								
	2 hours								
6	Predose			X	X				
	2 hours								
7	Predose								
	2 hours								
8	Predose								
	2 hours								

Table continued on next page

Day	Time Point	Pharmacokinetics ASP8062/metabolites	Pharmacokinetics Morphine/metabolites	Vital Signs	Clinical Laboratory Tests	12-lead ECG	ARCI-49	Spot End Tidal CO ₂	Spot SpO ₂
9	Predose	X		X	X	X	X	X	X
	0.25 hour	X							
	0.5 hour	X							
	1 hour	X		X				X	X
	1.5 hours	X							
	2 hours	X		X	X	X	X	X	X
	2.5 hours	X							
	3 hours	X							
	4 hours	X		X		X	X	X	X
	6 hours	X							
	8 hours	X		X			X	X	X
	12 hours	X		X		X	X		X
	16 hours	X							
10	Predose	X	X	X	X	X	X	X	X
	0.25 hour	X	X						
	0.5 hour	X	X						
	1 hour	X	X	X				X	X
	1.5 hours	X	X						
	2 hours	X	X	X	X	X	X	X	X
	2.5 hours	X							
	3 hours	X	X						
	4 hours	X	X	X		X	X	X	X

Table continued on next page

Day	Time Point	Pharmacokinetics ASP8062/metabolites	Pharmacokinetics Morphine/metabolites	Vital Signs	Clinical Laboratory Tests	12-lead ECG	ARCI-49	Spot End Tidal CO ₂	Spot SpO ₂
10	6 hours	X							
	8 hours	X	X	X			X	X	X
	12 hours	X	X	X		X	X		X
	16 hours	X	X						
11	24 hours postdose day 10	X	X	X	X		X		
	36 hours postdose day 10	X	X						
12	48 hours postdose day 10	X	X	X	X				
	60 hours postdose day 10	X							
13	72 hours postdose day 10	X		X	X				
14	96 hours postdose day 10	X		X	X				
15	120 hours postdose day 10	X		X	X				
16	144 hours postdose day 10	X		X	X	X			
ESV	5 to 9 days after the day 16 pharmacokinetic sample/ED/ET	X		X	X	X			

ARCI-49: 49-item short form of Addiction Research Center Inventory scale; CO₂: carbon dioxide; ECG: electrocardiogram; ED: early discontinuation; ESV: end-of-study visit; ET: early termination; SpO₂: blood oxygen saturation

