6.8 Concomitant Therapy

All medicinal products, including prescribed and nonprescribed drugs used prior to IP administration will be considered previous medication.

Specific restrictions on previous medications are provided in [Section 5.2 Exclusion Criteria].

All medication taken within 4 weeks prior to admission to the clinical unit will be documented.

All medicinal products other than the IP(s), including prescribed or nonprescribed drugs (including vitamins and natural and herbal remedies, e.g., St. John's Wort), used from first IP administration until the ESV will be considered concomitant medication.

Participants will only be allowed to use the following concomitant medication, if needed, from first IP administration until the ESV:

- Acetaminophen (up to 2 g/day)
- Topical dermatological products, including corticosteroid products
- Hormonal contraceptives
- HRT

If a participant's health condition necessitates the use of any medication other than the permitted medications during the study, an investigator and medical monitor, or designee(s), will discuss the case and determine if the participant should be withdrawn from the study and/or excluded from analysis sets, depending on if, and how, the medication(s) used influence(s) the study outcome. The nonpermitted concomitant medication will be recorded as a protocol deviation.

All concomitant treatments (medication and nonmedication therapy) will be documented.

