8.1 Discontinuation of Individual Participant(s) from Study Treatment

A discontinuation from treatment is defined as a participant who enrolled in the study and for whom study treatment is permanently discontinued for any reason.

The participant is free to withdraw from the study treatment and/or study for any reason and at any time without giving reason for doing so and without penalty or prejudice. The investigator is also free to discontinue the participant from study treatment or to terminate a participant's involvement in the study at any time if the participant's clinical condition warrants it.

The reason for discontinuation from study treatment must be documented in the participant's medical records.

A participant must discontinue study treatment for any of the following reasons:

- Participant requests to stop treatment
- Any clinical AE, laboratory abnormality or intercurrent illness, in the opinion of the investigator, indicates continued treatment is not in the best interest of the participant

- Female participant becomes pregnant
- If participant experiences symptomatic decrease in SpO₂ requiring medical intervention prior to day 10 (predose)

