8.2 Discontinuation of Individual Participant(s) from Study

All participants who discontinue study treatment will remain in the study and must continue to be followed for protocol-specific follow-up procedures as outlined in the Schedule of Assessments [Table 1]. The only exception to this is when the participant specifically withdraws consent for any further contact with him/her or persons previously authorized by the participant to provide this information.

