9.4.3.1 Adverse Events

AEs will be coded using MedDRA. An AE with onset at any time from first dosing until last scheduled procedure will be classified as a treatment-emergent adverse event (TEAE) for inclusion in the summary tabulations. An IP-related TEAE is defined as any TEAE with a causal relationship assessed as “yes” by the investigator, or records where the relationship is missing.

An overview and separate summaries of the number and percentage of participants with TEAEs, IP-related TEAEs, TEAEs leading to withdrawal of treatment, IP-related TEAEs leading to withdrawal of treatment and TEAEs excluding SAEs that equal or exceed a threshold of 5% in any treatment group will be presented by SOC, preferred term and treatment group. Also included in the overview are the number and percentage of participants with serious TEAEs, IP-related serious TEAEs, TEAEs leading to death and IP-related TEAEs leading to death.

The number and percentage of participants who have a TEAE within the drug abuse dependence Standardized MedDRA Queries (SMQ) (MedDRA v22.0) as classified by SOC

and preferred term, will be summarized by treatment group. In addition, the number and percentage of participants who have drug abuse-related TEAEs as classified by preferred term and lowest level term will be summarized by treatment group [Section 10.10 Appendix 10 Adverse Events of Interest Related to Potential Substance Abuse and Following Drug Withdrawal].

The number and percentage of participants who have a TEAE with the drug withdrawal SMQ (MedDRA v22.0) as classified by SOC and preferred term will be summarized by treatment group. In addition, the number and percentages of participants who have withdrawal-related TEAEs as classified by SOC and preferred term will be summarized by treatment group [Section 10.10 Appendix 10 Adverse Events of Interest Related to Potential Substance Abuse and Following Drug Withdrawal].

AE data will be listed.

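### Sections 8.1 and 6.8 open exits from the study that section 8.2 rules out, and anyone who leaves by them is not actively followed for new adverse events after a same-day end-of-study visit

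*Combined protocol and SAP*

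**What the plan says.** Section 8.2 sets the general rule: "All participants who discontinue study treatment will remain in the study and must continue to be followed for protocol-specific follow-up procedures", as laid out in Table 1. It then closes the list of exits: "The only exception to this is when the participant specifically withdraws consent for any further contact with him/her", or with persons the participant had authorised.

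Two other sections describe exits that need no withdrawal of consent:

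- Section 8.1 leaves the investigator free to "terminate a participant's involvement in the study at any time if the participant's clinical condition warrants it". This stands beside, and separate from, the power to stop study treatment.
- Section 6.8 permits only acetaminophen (up to 2 g/day), topical dermatological products, hormonal contraceptives and hormone replacement therapy. If anything else is needed, the investigator and medical monitor discuss the case and "determine if the participant should be withdrawn from the study", excluded from analysis sets, or both.

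The timing of the last visit comes from Table 1. Footnote 3 says: "If a participant discontinues early from the study, discharge/ESV procedures will be performed upon discontinuation". Footnote 4 puts the end-of-study visit (ESV) 5 to 9 days after the day 16 pharmacokinetic sample, or at early discontinuation or termination from the study.

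Section 7.3.1 collects adverse events (AEs) from consent to the follow-up visit and places no duty on investigators to look for events after participation ends. Section 9.4.3.1 sets the analysis window: "An AE with onset at any time from first dosing until last scheduled procedure will be classified as a treatment-emergent adverse event".

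**The concern.** Site staff cannot apply 8.1, 8.2 and 6.8 together as written. If a participant's clinical condition leads the investigator to end participation, or a drug outside the permitted list leads to withdrawal under 6.8, then 8.2 says the participant stays in follow-up and the other section says the participant may leave.

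The choice matters for the data. A participant who leaves has the final laboratory tests, ECG, C-SSRS and AE check on the day of exit. AEs, laboratory tests, ECG and C-SSRS are all primary endpoints. Section 9.4.3.1 also plans summaries of withdrawal-related events, and Appendix 10 lists events occurring after drug withdrawal. A visit on the day of leaving, with the last dose recent, cannot capture events that begin after stopping. The people most likely to leave by these routes are those who became unwell or needed treatment, for whom later events are of most interest.

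**Working it through.** **Reading the passages together.** Section 8.2 governs stopping *treatment*; footnotes 3 and 4 govern leaving the *study*. If only those who withdraw consent could leave, the footnotes would be consistent with 8.2. The contradiction is therefore between 8.2 on one side and 8.1 and 6.8 on the other. The footnotes supply the consequence.

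**Inputs.** Screening up to 28 days, dosing on days 1 to 10, discharge on day 16 and ESV 5 to 9 days later (synopsis and Table 1); half-life about 60 h (section 4.2); 24 enrolled for at least 18 completers (section 9.2); 2:1 allocation (section 6.3.6.2). The range of 48 to 72 h for the half-life is my assumption, to show sensitivity.

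**The plan's own figure.** 28 + 16 + 9 = 53 days, which reproduces the stated duration of about 53 days per participant. With the earliest ESV it is 28 + 16 + 5 = 49.

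**Completers' interval.** Day 16 is 144 h, or 6 days, after the day 10 dose. Then 6 + 5 = 11 days (264 h) and 6 + 9 = 15 days (360 h). In half-lives: 264/60 = 4.4 and 360/60 = 6.0.

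**Drug remaining after the last dose.** Fraction = 2^(−h/t½), one-compartment, ignoring absorption.

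| Time after last dose | t½ = 60 h | t½ = 48 to 72 h |
|---|---|---|
| 0 h | 100% | 100% |
| 24 h | 76% | 71% to 79% |
| 264 h | 4.7% | 2.2% to 7.9% |
| 360 h | 1.6% | 0.6% to 3.1% |

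**Level at exit relative to the day 10 level.** Just after dose n the ratio is (1 − 2^(−24n/60)) / (1 − 2^(−240/60)).

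- Dose 1: 0.242/0.938 = 26%
- Dose 3: 60%
- Dose 5: 80%
- Dose 6: (1 − 2^(−2.4))/(1 − 2^(−4)) = 86%
- Dose 8: 95%
- Dose 9: 98%

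After day 10 the level falls to 57% at 48 h, 33% at 96 h and 19% at 144 h (day 16).

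**Number affected.** 24 − 18 = 6 is the planning allowance for all non-completers. The documents give no figure for removals under 8.1 or 6.8.

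**Sensitivity of the summaries.** If all 24 are randomised 2:1, the arms are 16 and 8. One participant with an event term that is not captured moves that term's percentage by 1/16 = 6.25 points on ASP8062 or 1/8 = 12.5 points on placebo.

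**The case against.** The strongest reply is that the default path is sound and that several safeguards apply to those who leave.

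An AE that makes continued treatment unsuitable is listed in 8.1 as a reason to discontinue study *treatment*. Under 8.2 that participant stays and is followed. A same-day ESV arises only if the investigator also ends participation, or if the discussion under 6.8 ends in withdrawal from the study, which is one discretionary outcome among others. This stands: a reader might infer that anyone stopped for an AE on, say, day 6 has the final visit that day, and the documents do not say so.

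A reader might also infer that AE collection closes altogether. It does not:

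- Section 7.3 keeps the investigator responsible for events that are serious, related, or caused discontinuation.
- Section 7.3.3 follows serious events and those of special interest until they resolve or stabilise. Section 7.3.6 counts suicide- and abuse-related events among the latter.
- Sections 7.3.1 and 7.3.3 require notification of related serious events learned of later, and 7.3.3 also covers related events generally and AEs that progress to serious.
- Appendix 4 has its own repeat-testing rule for confirmed liver abnormalities.

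What remains after this reply is the conflict of wording and one gap: nobody is asked to look for *new* events after such an exit.

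**Conclusion.** The contradiction between 8.2 and sections 8.1 and 6.8 is established on the text. Its consequence is real but limited: for participants removed without withdrawing consent for contact, new events after the exit visit are not actively sought and fall outside the treatment-emergent window, while completers are observed for 11 to 15 days after the last dose. This takes the exit-day ESV as that participant's last scheduled procedure, which is the natural reading of footnotes 3 and 4 with 9.4.3.1.

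Three stronger readings are not supported:

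- **That the window closes at peak exposure.** Only those leaving on about days 8 to 10 are near the day 10 level; it is about 26% after dose 1 and 19% by day 16. The supportable statement is that substantial drug remains for those leaving during or soon after dosing.
- **That up to 6 participants (25%) are affected.** That allowance also includes participants who withdraw consent, whom 8.2 itself releases.
- **That ASP8062 event counts will be understated.** This would need more removals on ASP8062, which nothing in the documents indicates. A participant removed for a treatment-emergent event is already in the overall incidence; only further terms could be missed.

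The exposure figures rest on first-order, one-compartment decline. No sample size or error rate depends on this point. It is a low-cost improvement to the primary safety data.

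**What to change.** Reconcile sections 8.1, 8.2 and 6.8 and Table 1 footnotes 3 and 4 so that they give one account of who may leave the study and on what grounds. Which withdrawal rule applies is for the sponsor to decide.

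Whatever rule is chosen, for participants who leave early without withdrawing consent for contact:

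- keep the discharge procedures at exit;
- add an AE and serious AE contact, by visit or telephone, at the same interval after the last dose as the completers' ESV (11 to 15 days);
- state in 7.3.1 and 9.4.3.1 that events up to that contact are collected and counted as treatment-emergent.

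A telephone contact recovers reported events, including suicidality if asked about, but not laboratory or ECG findings. The sponsor should say which data are wanted after early exit. The cost is protocol wording and one extra visit or call for a few participants.

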3 OBJECTIVES, ENDPOINTS AND ESTIMANDS

Table 3 Study Objectives and Endpoints

Objectives	Endpoints
Primary	
• To assess the safety and tolerability of multiple doses of ASP8062 or placebo alone and in combination with a single dose of morphine• Nature, frequency and severity of AEs• Clinical laboratory tests (hematology, biochemistry and urinalysis)• Vital signs (blood pressure, pulse and respiratory rate)• 12-lead ECG• C-SSRS• SpO₂• End tidal CO₂
Secondary	
• To assess the potential for pharmacokinetic interaction between ASP8062 and morphine• Plasma ASP8062: AUC₂₄ and C_{max}• Plasma morphine and its metabolites (M3G and M6G): AUC_{inf}, AUC_{last} and C_{max}
Exploratory	
• To assess additional safety and tolerability of multiple doses of ASP8062 or placebo alone and in combination with a single dose of morphine• Oral temperature• ARCI-49• To assess the general pharmacokinetic parameters of ASP8062, its metabolites, morphine and its metabolites• Plasma ASP8062: CL/F, t_{1/2}, t_{max}, t_{lag}, V_z/F, C_{trough} and PTR• Plasma ASP8062 metabolites (AS3486189, AS3486191 and AS3486192): C_{max}, AUC₂₄, t_{1/2}, t_{max}, t_{lag}, V_z/F, C_{trough} and PTR• Plasma morphine and its metabolites (M3G and M6G): AUC_{inf}(%extrap), CL/F (morphine), t_{1/2}, t_{max}, t_{lag} and V_z/F• Plasma ASP8062 metabolites (AS3486189, AS3486191 and AS3486192): AUC₂₄ and C_{max}

AE: adverse event; ARCI-49: 49-item short form of Addiction Research Center Inventory scale; CO₂: carbon dioxide; C-SSRS: Columbia-suicide severity rating scale; ECG: electrocardiogram; M3G: morphine-3β-D-glucuronide; M6G: morphine-6β-D-glucuronide; SpO₂: blood oxygen saturation

Estimands

Not applicable.

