4 STUDY DESIGN AND DOSE RATIONALE

4.1 Overall Study Design

This will be a randomized, participant- and investigator-blinded, placebo-controlled, single sequence study comprising of male and female recreational opioid-using participants.

Approximately 24 male and female participants will be randomly assigned to complete at least 18 participants. An attempt will be made to enroll 1 female participant for every 3 male participants. The study will be conducted at 1 study site in the US.

Participants will be screened for up to 28 days prior to first investigational product (IP) administration. Eligible participants will be admitted to the clinical unit on day -1 and will be residential for a single period of 17 days/16 nights. After randomization, participants will receive multiple oral doses of ASP8062 or placebo (2:1 ratio) on days 1 through 10. On day 10, all participants will also receive a single oral dose of morphine immediately after the ASP8062 or placebo dose followed by a 144-hour in-house blood sampling period.

Scheduled safety and tolerability assessments will be conducted as indicated in the Schedule of Assessments [Table 1]. Participants are to remain awake, seated or semirecumbent and avoid lying on either the left or right side for at least 4 hours postdose on days 9 and 10.

Participants will be discharged from the clinical unit on day 16 on the condition that all required assessments have been performed and that there are no medical reasons for a longer stay in the clinical unit.

The study will be completed with an end-of-study visit (ESV). The ESV will take place 5 to 9 days after the day 16 pharmacokinetic sample is collected or at early discontinuation/termination from the study.

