9.4.3 Analysis of Safety

For analysis of safety, the treatment groups are (ASP8062 alone, placebo alone, morphine in combination with ASP8062, morphine in combination with placebo).

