9.4.3.6 Columbia-Suicide Severity Rating Scale

The listings will include only C-SSRS assessments that show at least 1 event of suicidality (suicidal ideation and/or suicidal behavior).

9.4.3.7 49-item Short Form of Addiction Research Center Inventory Scale

From the completed ARCI-49 questionnaire, scores for the amphetamine, benzedrine, pentobarbital-chlorpromazine-alcohol, morphine-benzedrine and lysergic-acid-diethylamide groups will be calculated. The calculated subscale score and change from baseline will be listed and summarized by treatment group and time point.

The algorithm for scoring the ARCI-49 [Martin et al, 1971] is presented in [Section 10.9 Appendix 9 49-item Short Form of Addiction Research Center Inventory Scale, Questionnaire Scoring]. One point will be given for each response that agrees with the scoring direction. Specifically, 1 point will be given for each "true" response (i.e., item has associated scoring coefficient +1), and 1 point will be given for each "false" response in the

reverse-scored items (i.e., item has associated scoring coefficient -1). Each subscale score will be derived as the linear combination (sum) of mathematically-signed points among the relevant items, i.e., matched true/false responses. Some items belong to more than 1 subscale.

No missing data will be imputed.

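### The day 16 C-SSRS looks back to day 9, so its recall interval mixes up to about 24 h before morphine with the 144 h after coadministration, and an undated positive item cannot be placed reliably in either period

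*Combined protocol and SAP*

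**What the plan says.** C-SSRS is one of the primary endpoints in Table 3 (Section 3). The objective it serves is "To assess the safety and tolerability of multiple doses of ASP8062 or placebo alone and in combination with a single dose of morphine". Section 9.4.3 carries that division into the analysis: "the treatment groups are (ASP8062 alone, placebo alone, morphine in combination with ASP8062, morphine in combination with placebo".

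Footnote 15 to Table 1 gives the Baseline/Screening form at screening and fixes "the version of the C-SSRS to be performed on days -1, 9 and 16 and at the ESV" as the Since Last Visit form. Table 1 has no C-SSRS on day 10, and Table 2 has no C-SSRS column, so no clock time is given for any rating.

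Section 4.1 places the coadministration: "On day 10, all participants will also receive a single oral dose of morphine immediately after the ASP8062 or placebo dose". Footnote 2 to Table 1 places day 16 relative to it: "Scheduled sampling up to day 16 (144 hours postdose of morphine". Footnote 4 places the end-of-study visit (ESV): "The ESV will take place 5 to 9 days after the day 16 pharmacokinetic sample is collected".

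The only C-SSRS output is in Section 9.4.3.6: "The listings will include only C-SSRS assessments that show at least 1 event of suicidality". That section does not say how a listed assessment is assigned to one of the four groups.

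**The concern.** A Since Last Visit form reports whether something happened at any time since the previous form. What it can say about a treatment period depends on where its interval begins and ends. Here the interval that contains the morphine dose opens on day 9, while participants are still on ASP8062 or placebo alone, and closes on day 16. The first interval that lies wholly after morphine opens only on day 16.

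The form does little to resolve this. In Appendix 8 the ideation items are yes/no with a free-text description, and the only date requested is for actual attempts. A yes to an ideation item on day 16 could refer to day 9 or to any later day.

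At stake is the attribution of an individual positive. Section 7.3.6 treats suicide-related events as a concern specific to ASP8062, so whether even one case arose on ASP8062 alone or after morphine was added would be asked when the results are read.

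C-SSRS also differs here from the other scheduled safety measures. Table 2 gives vital signs, laboratory tests, ECG, ARCI-49, spot end tidal CO2 and spot SpO2 a predose time point on day 10, which separates the two periods. C-SSRS, which depends on a recall window, has none.

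**Working it through.** **Inputs**

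- C-SSRS on days -1, 9, 16 and at the ESV (Table 1, footnote 15).
- Morphine on day 10, directly after the ASP8062 or placebo dose (Section 4.1).
- Day 16 is 144 h after morphine (Table 1, footnote 2).
- ESV 5 to 9 days after the day 16 sample (Table 1, footnote 4).
- Assumptions, because no C-SSRS clock times are given: doses on days 9 and 10 are 24 h apart; the day 16 form is completed at the 144 h point; the day 9 form is completed *h* hours after the day 9 dose, with *h* between 0 (predose) and 24 (just before the day 10 dose).

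**The plan's own figure.** (16 − 10) × 24 = 144 h, which agrees with footnote 2.

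**Recall interval of the day 16 form.** Hours before morphine = 24 − *h*. Total hours = (24 − *h*) + 144. Share before morphine = (24 − *h*) / (168 − *h*).

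| Day 9 form completed | Hours before morphine | Total hours | Share before morphine |
|---|---|---|---|
| Predose (*h* = 0) | 24 | 168 | 14.3% |
| *h* = 8 | 16 | 160 | 10.0% |
| *h* = 12 | 12 | 156 | 7.7% |
| *h* = 16 | 8 | 152 | 5.3% |
| Just before the day 10 dose (*h* = 24) | 0 | 144 | 0% |

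**The neighbouring intervals.** The day 9 form covers day -1 to day 9. It contains no morphine exposure, but it opens before the first study dose. The ESV form lies wholly after morphine. It opens at 144 h and closes between 144 + 5 × 24 = 264 h and 144 + 9 × 24 = 360 h after the dose.

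**With the form moved to predose on day 10.** The day 16 interval becomes 144 of 144 h after coadministration. The day 10 form covers day -1 to the day 10 dose: all before morphine, but still including the short time between the day -1 form and the first dose.

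**The case against.** The strongest reply is that little in the planned analysis depends on this. Vital signs, SpO2, ARCI-49 and end tidal CO2 are each to be summarized by treatment group and time point; C-SSRS is not. Its only output is a listing of positives, and the four-group sentence in Section 9.4.3 is general. A reader might infer that this primary endpoint cannot be split by treatment as the plan intends. The documents do not support that, because no C-SSRS table exists that would fail. A reader might also infer that a day 16 positive would be listed under the combination. No passage says so; the plan is silent on labelling.

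Other information may date an event. Positive ideation, attempt and preparatory items ask for a description, and actual attempts ask for a date (Appendix 8). Participants are resident through day 16 (Section 4.1), adverse events are assessed daily (Section 2.3.1), and suicide-related events are of special interest, with extra information gathered for narratives (Section 7.3.6). With about 24 participants, and suicidal ideation in the previous 12 months excluded (exclusion criterion 11), few positives are likely, and a narrative could often place the onset.

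It is also true that 24 h is the maximum overlap, that both randomized arms have identical intervals, and that even a clean day 16 interval would span six days although morphine sampling stops at 48 h (Table 2).

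All of this limits the consequence, and most of it stands. It does not remove the gap. A description need not contain a date, and an adverse event supplies an onset date only if the item is also recorded as one. The plan requires neither that nor a reconciliation of C-SSRS with adverse event records.

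**Conclusion.** The point holds as a minor gap in the schedule. The day 16 recall interval includes up to about 24 h of the alone period (at most 14.3% of 168 h), and a positive ideation item on that form cannot be placed reliably before or after morphine from the form itself. Only the within-arm reading of alone against combination is blurred, and only for listed day 16 positives. The contrast of ASP8062 plus morphine with placebo plus morphine is not affected.

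The size rests on the assumed clock times; the overlap disappears only if the day 9 form is completed just before the day 10 dose. That positives will be rare is an expectation from the eligibility criteria and the sample size, not a figure in the plan. The change is worth making because it costs almost nothing, not because the primary objective is at risk.

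**What to change.** In Table 1 and footnote 15, move the day 9 C-SSRS to predose on day 10, before the ASP8062 or placebo dose and before morphine. The day 16 and ESV forms then cover only time after coadministration, and the day 10 form covers only time before morphine (from day -1, so it should not be described as covering dosing time only). Stating predose also settles the missing clock time.

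In Section 9.4.3.6, add one sentence: listed positives from day 10 are labelled alone, and those from day 16 and the ESV are labelled combination, each within the participant's arm.

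Cost: no questionnaire is added. One short questionnaire moves from day 9 into the day 10 predose block, where Section 7.2.9 allows 60 minutes for procedures. None of the treatment discontinuation reasons in Section 8.1 refers to a day 9 C-SSRS. Adding the labelling sentence without moving the form would make the listing consistent, but it would not show in which period a day 16 positive arose.
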